## Table 14.3.1.2.1 Summary of Treatment Emergent Adverse Events by System Organ Class and Preferred Term – Monotherapy Period (Safety Population)

Adverse Events [1,2,3,4]	Statistic	ZOF 30 mg (N=xx)	AML 5 mg (N=xx)	All Patients (N=xx)
Total Number of TEAEs	n	XX	XX	xx
Number of Patients with at Least One TEAE	n (%)	xx (xx.x)	xx (xx.x)	xx (xx.x)
System Organ Class #1	n (%)	xx (xx.x)	xx (xx.x)	xx (xx.x)
Preferred Term #1	n (%)	xx (xx.x)	xx (xx.x)	xx (xx.x)
Preferred Term #2	n (%)	xx (xx.x)	xx (xx.x)	xx (xx.x)
Preferred Term #3	n (%)	xx (xx.x)	xx (xx.x)	xx (xx.x)
etc.				
System Organ Class #2	n (%)	xx (xx.x)	xx (xx.x)	xx (xx.x)
Preferred Term #1	n (%)	xx (xx.x)	xx (xx.x)	xx (xx.x)
Preferred Term #2	n (%)	xx (xx.x)	xx (xx.x)	xx (xx.x)
Preferred Term #3	n (%)	xx (xx.x)	xx (xx.x)	xx (xx.x)
etc.				

[1] AE: Adverse Event. Defined as any untoward medical occurrence in a clinical trial patient administered a medicinal product and which does not necessarily have a causal relationship with this treatment.

[2] TEAE: Treatment Emergent Adverse Event. Defined as AEs that occur after the first dose of monotherapy of ZOF or AML.

[3] Patients will be counted once per System Organ Class/Preferred Term (SOC/PT).

[4] MedDRA Dictionary version XX.X was used to code adverse events.

Source: Listings 16.2.7.1, 16.2.7.2, 16.2.7.3

Program Name: XXXX.SAS

Date: DDMMMYYYY

- For the combined therapy period tables presented in the list below: Patients will be classified as either ZOF/AML 30/5 mg or ZOF/AML 30/10 mg such that no patients are counted in both groups. That is, even though patients in the ZOF/AML 30/10 mg group are also exposed to the ZOF/AML 30/5 mg treatment, they will only be included in the ZOF/AML 30/10 mg and All Patients columns, not within the ZOF/AML 30/5 mg column. Patients that do not belong to the ZOF/AML 30/5 mg or ZOF/AML 30/10 mg group will be included only in the All Patients column.
- Repeat for the following tables:
  - 14.3.1.2.2 Summary of Treatment Emergent Adverse Events by System Organ Class and Preferred Term Combined Therapy Period Safety Population
     In the column headers, "ZOF 30 mg" and "AML 5mg" will change to "ZOF/AML 30/5 mg [4]" and "ZOF/AML 30/10 mg [4]", respectively.
  - 14.3.1.3.1 Summary of Treatment Emergent Severe Adverse Events by System Organ Class and Preferred Term Monotherapy Period Safety Population
    - Rows 1 and 2 will change from TEAE(s) to Severe TEAE(s).
  - 14.3.1.3.2 Summary of Treatment Emergent Severe Adverse Events by System Organ Class and Preferred Term Combined Therapy Period Safety Population

Statistical Analysis Plan

0

- Rows 1 and 2 will change from TEAE(s) to Severe TEAE(s).
- In the column headers, "ZOF 30 mg" and "AML 5mg" will change to "ZOF/AML 30/5 mg [4]" and "ZOF/AML 30/10 mg [4]", respectively.
- 14.3.1.4.1 Summary of Adverse Drug Reactions by System Organ Class and Preferred Term Monotherapy Period Safety Population
  - Rows 1 and 2 will change from TEAE(s) to ADR(s).
  - In the column headers, "ZOF 30 mg" and "AML 5mg" will change to "ZOF/AML 30/5 mg [4]" and "ZOF/AML 30/10 mg [4]", respectively.
  - Footnote [2] will change to [ADR: Adverse Drug Reaction. Defined as AEs that have a relationship of "certain," "probable," "possible," or "unassessable."]
- o 14.3.1.4.2 Summary of Adverse Drug Reactions by System Organ Class and Preferred Term Combined Therapy Period Safety Population
  - Rows 1 and 2 will change from TEAE(s) to ADR(s).
  - In the column headers, "ZOF 30 mg" and "AML 5mg" will change to "ZOF/AML 30/5 mg [4]" and "ZOF/AML 30/10 mg [4]", respectively.
  - Footnote [2] will change to [ADR: Adverse Drug Reaction. Defined as AEs that have a relationship of "certain," "probable," "possible," or "unassessable."]
- 14.3.1.5.1 Summary of Treatment Emergent Adverse Events Leading to Study Discontinuation by System Organ Class and Preferred Term Monotherapy Period – Safety Population
  - Rows 1 and 2 will change from TEAE(s) to TEAE(s) Leading to Study Discontinuation.
- 14.3.1.5.2 Summary of Treatment Emergent Adverse Events Leading to Study Discontinuation by System Organ Class and Preferred Term Combined Therapy Period – Safety Population
  - Rows 1 and 2 will change from TEAE(s) to TEAE(s) Leading to Study Discontinuation.
  - In the column headers, "ZOF 30 mg" and "AML 5mg" will change to "ZOF/AML 30/5 mg [4]" and "ZOF/AML 30/10 mg [4]", respectively.
- o 14.3.2.1.1 Summary of Treatment Emergent Serious Adverse Events by System Organ Class and Preferred Term Monotherapy Period Safety Population
  - Rows 1 and 2 will change from TEAE(s) to TESAE(s).
  - Footnote [2] will change to "TESAE: Treatment Emergent Serious Adverse Event."
- 14.3.2.1.2 Summary of Treatment Emergent Serious Adverse Events by System Organ Class and Preferred Term Combined Therapy Period Safety Population
  - Rows 1 and 2 will change from TEAE(s) to TESAE(s).
  - In the column headers, "ZOF 30 mg" and "AML 5mg" will change to "ZOF/AML 30/5 mg [4]" and "ZOF/AML 30/10 mg [4]", respectively.
  - Footnote [2] will change to "TESAE: Treatment Emergent Serious Adverse Event."
- o 14.3.2.2.1 Summary of Serious Adverse Drug Reactions by System Organ Class and Preferred Term Monotherapy Period Safety Population
  - Rows 1 and 2 will change from TEAE(s) to Serious ADR(s).
  - Footnote [2] will change to [Serious ADR: Serious Adverse Drug Reaction. Defined as SAEs that have a relationship of "certain," "probable,"
     "possible," or "unassessable."]
- 14.3.2.2.2 Summary of Serious Adverse Drug Reactions by System Organ Class and Preferred Term Combined Therapy Period Safety Population
  - Rows 1 and 2 will change from TEAE(s) to Serious ADR(s).
  - In the column headers, "ZOF 30 mg" and "AML 5mg" will change to "ZOF/AML 30/5 mg [4]" and "ZOF/AML 30/10 mg [4]", respectively.
  - Footnote [2] will change to [Serious ADR: Serious Adverse Drug Reaction. Defined as SAEs that have a relationship of "certain," "probable,"
     "possible," or "unassessable."]
- 14.3.2.3.1 Summary of Treatment Emergent Serious Adverse Events with Outcome of Death by System Organ Class and Preferred Term Monotherapy Period – Safety Population
  - Rows 1 and 2 will change from TEAE(s) to TESAE(s) with Outcome of Death.
  - Footnote [2] will change to "TESAE: Treatment-Emergent Serious Adverse Event."
- 14.3.2.3.2 Summary of Treatment Emergent Serious Adverse Events with Outcome of Death by System Organ Class and Preferred Term Combined Therapy Period – Safety Population

- Rows 1 and 2 will change from TEAE(s) to TESAE(s) with Outcome of Death.
- In the column headers, "ZOF 30 mg" and "AML 5mg" will change to "ZOF/AML 30/5 mg [4]" and "ZOF/AML 30/10 mg [4]", respectively.
- Footnote [2] will change to "TESAE: Treatment-Emergent Serious Adverse Event."

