### 5.2.2 First Dose

First dose is defined as the first administration of the extemporaneous combination of ZOF 30 mg and AML 5 mg that occurs on Visit 2 (Baseline). Monotherapies taken prior to Visit 2 should not be considered when defining first dose.

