### 8 Safety Analyses (Endpoint 2.5)

**Endpoint 2.5**: Safety and tolerability of the monotherapies (ZOF 30 mg and AML 5 mg) after 4 weeks of therapy and of the extemporaneous combination (ZOF 30 mg and AML 5 mg or AML 10 mg) after eight weeks of treatment.

The variables for endpoint 2.5 are laboratory tests, physical examination, vital signs, 12-lead ECG, and incidence of AEs/SAEs, each of which are discussed in the subsections below.

Safety analyses will be performed on the SAF population. Results will be presented as described in section 5.5 unless otherwise specified.

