### 8.2 Adverse Events, Adverse Drug Reactions, and Deaths

Adverse Events (AEs) are any untoward medical occurrence in a clinical trial patient administered a medicinal product and which does not necessarily have a causal relationship with this treatment.

*Treatment Emergent AEs (TEAEs)* are defined as AEs that occur only once treatment has started (after the first dose of monotherapy of ZOF or AML). Thus, all AEs that occur in both the monotherapy and combined therapy periods will be considered treatment-emergent.

Adverse Drug Reactions (ADRs) are defined as AEs that have a relationship of "certain," "probable," "possible," or "unassessable."

All AEs will be coded using the Medical Dictionary for Regulatory Activities (MedDRA) version 24.1 or later.

The following tabulations will be produced for the monotherapy period and the combination therapy periods for the SAF population:

- Monotherapy Period (Day of Visit 1 through day before Day of Visit 2)
  - All treatment-emergent AEs (TEAEs)

- Severe TEAEs
- Adverse Drug Reactions (ADRs)
- TEAEs leading to study discontinuation
- Serious TEAEs (TESAEs)
- o Serious ADRs
- TESAEs with outcome of death
- Combination Therapy Period (Day of Visit 2 through Day of Visit 4)
  - All treatment-emergent AEs (TEAEs)
  - Severe TEAEs
  - Adverse Drug Reactions (ADRs)
  - TEAEs leading to study discontinuation
  - Serious TEAEs (TESAEs)
  - Serious ADRs
  - TESAEs with outcome of death

Key guidelines for counting incidence proportions of AEs/TEAEs/ADRs (collectively referred to as AEs for the remainder of this section) are as follows:

- When a patient has the same AE reported multiple times during an analysis period based on MedDRA terminology (SOC or PT), the patient will only be counted once within a level of MedDRA in an AE incidence table.
- When assessing investigator reported relationship to study drug of the AEs, if an AE reported multiple times changes in causal relationship during an analysis period for a patient, the event with highest relatedness will be presented. Related AEs (i.e., ADRs) will include those reported as "certain," "probable," "possible," or "unassessable" by the investigator.

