- When summarizing severity of the AEs (mild, moderate, severe), if there are multiple AEs of the same preferred term but different severity during an analysis period for a patient, the AE with the maximum severity will be reported. If the AE term (SOC and PT) is reported more than once, one of them with missing severity, and at least another with non-missing severity, the maximum severity will be chosen from the non-missing severity and the missing severity can be ignored. If all are of missing severity, then the AE severity will be summarized with an additional "Missing" category. In summary of severe AEs, missing severity will be included in severe category following the conservative approach.

All AE tabulations for the monotherapy period will present the incidences separately for the monotherapy groups (ZOF 30 mg or AML 5 mg) and All Patients for the SAF population. That is, all patients who experienced at least one AE in the monotherapy period will be summarized together in the All Patients column of the corresponding summary tables. All patients who take ZOF 30 mg will be summarized in the ZOF 30 mg column and all patients who take AML 5 mg will be summarized in the AML 5 mg column.

All AE tabulations for the combined therapy period will present the incidences separately for the combined treatment groups (ZOF/AML 30/5 mg or ZOF/AML 30/10 mg) and All Patients for the SAF population. That is, all patients who experienced at least one AE in the combined therapy period will be summarized together in the All Patients column of the corresponding summary tables. All patients who take ZOF/AML 30/10 mg will be summarized in the ZOF/AML 30/10 mg column, even for AEs that occurred while taking the ZOF/AML 30/5 regimen. Lastly, all patients who take ZOF/AML 30/5 mg for the duration of the combined therapy period will be summarized in the ZOF/AML 5 mg column.

In summaries by SOC and PT (for both monotherapy and combined therapy periods), AEs will be sorted by descending frequency for SOC and PT in the All Patients column. All AEs will also be presented in bypatient data listings for Adverse Events for the SAF population.

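### The shell for Table 14.3.1.4.1 puts combination-dose column headers on monotherapy-period drug reactions, against SAP 8.2

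*SAP*

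**What the plan says.** SAP section 8 makes the safety of each single drug part of Endpoint 2.5: "Safety and tolerability of the monotherapies (ZOF 30 mg and AML 5 mg) after 4 weeks". SAP 8.2 then fixes the layout: "All AE tabulations for the monotherapy period will present the incidences separately for the monotherapy groups (ZOF 30 mg or AML 5 mg"), together with an All Patients column. ADRs fall under that rule. They are listed among the monotherapy-period tabulations, and the counting rules that precede the layout rule open with "Key guidelines for counting incidence proportions of AEs/TEAEs/ADRs (collectively referred to as AEs for the remainder of this section").

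SAP section 11 refers to the TLF shells for the mock layouts. Shell Table 14.3.1.2.1 (TEAEs by SOC/PT, monotherapy period) has ZOF 30 mg, AML 5 mg and All Patients columns. It ends with a list of tables that reuse the layout, each with its own edits. For the entry "14.3.1.4.1 Summary of Adverse Drug Reactions by System Organ Class and Preferred Term Monotherapy Period Safety Population", the list gives three edits: change the first two rows to ADRs, change footnote [2] to the ADR definition, and the following: "In the column headers, 'ZOF 30 mg' and 'AML 5mg' will change to 'ZOF/AML 30/5 mg [4]' and 'ZOF/AML 30/10 mg [4]', respectively".

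**The concern.** The header edit cannot be reconciled with SAP 8.2. A programmer who follows the shell produces a run-in table whose dose columns name treatments that nobody had started. Zofenopril reactions would stand under ZOF/AML 30/5 mg and amlodipine reactions under ZOF/AML 30/10 mg. The table would also carry the same dose headings as its combined-period partner, 14.3.1.4.2, while describing different treatment groups.

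At stake is how drug-related events on each monotherapy are reported by reaction type. Table 14.3.1.4.1 is the only planned SOC/PT table that covers all monotherapy-period ADRs, serious and non-serious together.

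**Working it through.** No arithmetic applies, because the point does not depend on any sample size, effect size or error rate. The check sets the texts side by side.

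**1. Could any event in this table have occurred on a combination?** SAP 8.2 defines the window as "Monotherapy Period (Day of Visit 1 through day before Day of Visit 2"). SAP 5.2.2 places the "first administration of the extemporaneous combination of ZOF 30 mg and AML 5 mg that occurs on Visit 2". The window closes the day before the first combination dose, so no event in the table can belong to 30/5 or 30/10.

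**2. Does the shell intend the 30/5 versus 30/10 split here?** The programming note under the same shell limits it: "For the combined therapy period tables presented in the list below: Patients will be classified as either ZOF/AML 30/5 mg or ZOF/AML 30/10 mg". The note's scope is the combined-period tables; 14.3.1.4.1 is titled as a monotherapy-period table.

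**3. Which tables in the repeat list carry the header edit?**

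| Content | Monotherapy-period table | Header edit? | Combined-period table | Header edit? |
|---|---|---|---|---|
| All TEAEs | 14.3.1.2.1 (parent shell) | not applicable | 14.3.1.2.2 | yes |
| Severe TEAEs | 14.3.1.3.1 | no | 14.3.1.3.2 | yes |
| **ADRs** | **14.3.1.4.1** | **yes** | 14.3.1.4.2 | yes |
| TEAEs leading to discontinuation | 14.3.1.5.1 | no | 14.3.1.5.2 | yes |
| Serious TEAEs | 14.3.2.1.1 | no | 14.3.2.1.2 | yes |
| Serious ADRs | 14.3.2.2.1 | no | 14.3.2.2.2 | yes |
| Fatal serious TEAEs | 14.3.2.3.1 | no | 14.3.2.3.2 | yes |

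All seven combined-period tables carry the edit, as they should. Of the six monotherapy-period repeats, one does. Its three bullets are the same as those under 14.3.1.4.2, which fits a block copied from the neighbouring entry. The closest analogue, the serious-ADR table 14.3.2.2.1, changes only its rows and footnote and keeps the single-drug columns.

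**4. Is it a declared change?** SAP section 10 lists changes to the analysis populations and to one exploratory analysis. It mentions no new grouping for monotherapy-period ADRs.

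**5. What remains correct?**
- The All Patients column of 14.3.1.4.1.
- Table 14.3.1.1.1, with the number of ADRs, patients with an ADR and patients with a serious ADR, by ZOF 30 mg and AML 5 mg.
- Table 14.3.1.2.1, with all monotherapy-period TEAEs by SOC/PT and single drug.
- Table 14.3.2.2.1, with serious ADRs by SOC/PT and single drug.
- Listings 16.2.7.1 (SOC/PT and therapy period), 16.2.7.2 (relationship) and 16.2.5.2 (run-in drug). Linked by patient, and by AE number for the two AE listings, they show which monotherapy each reacting patient was taking.

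**The case against.** The strongest reply is that this is a stray line in a mock-up. The SAP text gives the right rule, the table's title says monotherapy, the programming note limits the split to the other period, and an attentive programmer would notice. Most of the information also survives elsewhere, as step 5 shows. This reply stands as to size. It does not remove the contradiction: no rule was found that SAP text overrides the shells, and section 11 sends the programmer to the shells for layout.

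Three stronger readings are tempting, and the documents do not support them.

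- **Regrouping.** A reader might infer that run-in patients would be re-sorted by their later combination dose, so that patients withdrawn at Visit 2 drop out of both dose columns. The bullet changes headers only, and the classification note excludes monotherapy-period tables.
- **A count of affected patients.** A reader might take 290 − 216 = 74 as the number left without a dose column. That figure matters only under regrouping. The protocol synopsis and section 6 also describe the 290 as screened, with screening failures inside the 25% allowance, and screening failures are outside the Safety population. Protocol 12.2 instead calls the 290 enrolled, so the figure has no single meaning.
- **Half of Endpoint 2.5 lost, or the only table of related events.** Endpoint 2.5 also covers laboratory tests, physical examination, vital signs and ECG, and 14.3.2.2.1 separately tabulates serious monotherapy ADRs with correct columns.

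**Conclusion.** The point holds as an internal inconsistency of low severity. One bullet in the shells contradicts SAP 8.2 and the shell's own programming note. If it is programmed as written, both dose columns of Table 14.3.1.4.1 carry wrong labels.

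The damage is confined to the breakdown by single drug and reaction type of all monotherapy-period ADRs in that one table. Overall ADR counts by drug, the TEAE and serious-ADR breakdowns, and every efficacy result are unaffected. The conclusion assumes that the shell is followed literally and that only the headers change, which is all the bullet orders.

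**What to change.** Delete the header-change bullet under 14.3.1.4.1, so that the table keeps its ZOF 30 mg, AML 5 mg and All Patients columns. Leave the row and footnote edits for that table as they are, and keep the header change under 14.3.1.4.2.

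The cost is one line in the shells. No data, population, endpoint or design element changes. The edit brings the shells into line with SAP 8.2, and section 11 already says that minor layout changes to the TLFs need no SAP modification.

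While the list is open, check the [4] tag in the replacement headers of the combined-period tables. In this shell, footnote [4] gives the MedDRA version and does not describe a treatment group.

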#### Table 14.3.4.1.1 Summary and Change from Baseline (Visit 1) to Visit 4 for Haematology Parameters (Safety Population)

			ZOF/AML 30/5 mg	ZOF/AML 30/10 mg	All Patients
Parameter (Unit)	Visit [1]	Statistic	(N=xx)	(N=xx)	(N=xx)
xxxxxxx (xxx)	Baseline (Visit 1)	n	xx	xx	ХХ
		Mean (SD)	xx.x (xx.xx)	xx.x (xx.xx)	xx.x (xx.xx)
		Median	xx.x	xx.x	xx.x
		Min, Max	xx, xx	xx, xx	xx, xx
	Visit 4	n	XX	xx	xx
		Mean (SD)	xx.x (xx.xx)	xx.x (xx.xx)	xx.x (xx.xx)
		Median	xx.x	xx.x	xx.x
		Min, Max	xx, xx	xx, xx	xx, xx
	Visit 4 CFB	n	XX	XX	xx
		Mean (SD)	xx.x (xx.xx)	xx.x (xx.xx)	xx.x (xx.xx)
		Median	xx.x	xx.x	xx.x
Repeat for All Parameters		Min, Max	xx, xx	xx, xx	xx, xx

[1] CFB = Change from Baseline. Visit 1 values will serve as Baseline since laboratory parameters are not assessed at Visit 2.
 Source: Listing 16.2.8.1
 Program Name: XXXX.SAS

Date: DDMMMYYYY

- Patients will be classified as either ZOF/AML 30/5 mg or ZOF/AML 30/10 mg such that no patients are counted in both groups. That is, even though patients in the ZOF/AML 30/10 mg group are also exposed to the ZOF/AML 30/5 mg treatment, they will only be included in the ZOF/AML 30/10 mg and All Patients columns, not within the ZOF/AML 30/5 mg column. Same for table in the list below.
- Repeat for the following tables:
  - o 14.3.4.1.2 Summary and Change from Baseline (Visit 1) to Visit 4 for Serum Chemistry Parameters Safety Population
    - Footnote for Source will change to "Source: Listing 16.2.8.2"
    - Source will change to Listing 16.2.8.2

#### Table 14.3.4.2.1 Shift from Baseline (Visit 1) to Visit 4 for Haematology Parameters (Safety Population)

					Baseline (Visit 1) Value	
Parameter (Unit)	Combined Therapy Group	Visit 4 Value	Statistic	Normal	Abnormal, NCS	Abnormal, CS
xxxxxxx (xxx)	ZOF/AML 30/5 mg (N=xxx)	Normal	n (%)	xx (xx.x)	xx (xx.x)	xx (xx.x)
		Abnormal, NCS	n (%)	xx (xx.x)	xx (xx.x)	xx (xx.x)
		Abnormal, CS	n (%)	xx (xx.x)	xx (xx.x)	xx (xx.x)
	ZOF/AML 30/10 mg (N=xxx)	Normal	n (%)	xx (xx.x)	xx (xx.x)	xx (xx.x)
		Abnormal, NCS	n (%)	xx (xx.x)	xx (xx.x)	xx (xx.x)
		Abnormal, CS	n (%)	xx (xx.x)	xx (xx.x)	xx (xx.x)
	All Patients (N=xxx)	Normal	n (%)	xx (xx.x)	xx (xx.x)	xx (xx.x)
Repeat for All		Abnormal, NCS	n (%)	xx (xx.x)	xx (xx.x)	xx (xx.x)
Parameters		Abnormal, CS	n (%)	xx (xx.x)	xx (xx.x)	xx (xx.x)

Source: Listing 16.2.8.1 Program Name: XXXX.SAS

Date: DDMMMYYYY

- Patients will be classified as either ZOF/AML 30/5 mg or ZOF/AML 30/10 mg such that no patients are counted in both groups. That is, even though patients in the ZOF/AML 30/10 mg group are also exposed to the ZOF/AML 30/5 mg treatment, they will only be included in the ZOF/AML 30/10 mg and All Patients sections, not within the ZOF/AML 30/5 mg section. Same for table in the list below.
- Repeat for the following tables:
  - o 14.3.4.2.2 Shift from Baseline (Visit 1) to Visit 4 for Serum Chemistry Parameters Safety Population
    - Source will change to Listing 16.2.8.2

#### Table 14.3.5 Summary of Study Drug Accountability, Exposure, and Adherence (Safety Population)

/isit	Parameter [1,2,3]	Statistic	ZOF 30 mg	AML 5 mg	AML 10 mg
Visit 1 (Week -4)	IP Dispensed (tablets)	n	xx	xx	
		Mean (SD)	xx.x (xx.xx)	xx.x (xx.xx)	
		Median	xx.x	xx.x	
		Min, Max	xx, xx	xx, xx	
/isit 2 (Week 0)	IP Dispensed (tablets)	n	хх	хх	
		Mean (SD)	xx.x (xx.xx)	xx.x (xx.xx)	
		Median	xx.x	xx.x	
		Min, Max	xx, xx	xx, xx	
	IP Returned (tablets)	n	xx	хх	
		Mean (SD)	xx.x (xx.xx)	xx.x (xx.xx)	
		Median	xx.x	xx.x	
		Min, Max	xx, xx	xx, xx	
	Adherence (%) Derived	n	хх	хх	
		Mean (SD)	xx.x (xx.xx)	xx.x (xx.xx)	
		Median	xx.x	xx.x	
		Min, Max	xx, xx	xx, xx	
	Adherence (%) CRF				
	< 80%	n/N (%)	xx/xx (xx.x)	xx/xx (xx.x)	
	≥ 80% and ≤ 120%	n/N (%)	xx/xx (xx.x)	xx/xx (xx.x)	
	> 120%	n/N (%)	xx/xx (xx.x)	xx/xx (xx.x)	
Visit 3 (Week 4)	IP Dispensed (tablets)	n	XX	XX	xx
		Mean (SD)	xx.x (xx.xx)	xx.x (xx.xx)	xx.x (xx.xx)
		Median	xx.x	xx.x	XX.X
		Min, Max	xx, xx	xx, xx	xx, xx
	IP Returned (tablets)	n	хх	хх	
		Mean (SD)	xx.x (xx.xx)	xx.x (xx.xx)	
		Median	xx.x	xx.x	
		Min. Max	XX. XX	XX. XX	

	Adherence (%) Derived				
	Individual IP	n	xx	xx	
		Mean (SD)	xx.x (xx.xx)	xx.x (xx.xx)	
		Median	xx.x	xx.x	
		Min, Max	xx, xx	xx, xx	
	Combined IP (ZOF/AML)	n		xx	
		Mean (SD)		xx.x (xx.xx)	
		Median		xx.x	
		Min, Max		xx, xx	
	Adherence (%) CRF				
	< 80%	n/N (%)		xx/xx (xx.x)	
	$\geq$ 80% and $\leq$ 120%	n/N (%)		xx/xx (xx.x)	
	> 120%	n/N (%)		xx/xx (xx.x)	
Visit 4 (Week 8)	IP Returned (tablets)	n	XX	хх	xx
		Mean (SD)	xx.x (xx.xx)	xx.x (xx.xx)	xx.x (xx.xx)
		Median	xx.x	xx.x	XX.X
		Min, Max	xx, xx	xx, xx	xx, xx
	Adherence (%) Derived				
	Individual IP	n	xx	xx	XX
		Mean (SD)	xx.x (xx.xx)	xx.x (xx.xx)	xx.x (xx.xx)
		Median	xx.x	xx.x	xx.x
		Min, Max	xx, xx	xx, xx	xx, xx
	Combined IP (ZOF/AML)	n		хх	xx
		Mean (SD)		xx.x (xx.xx)	xx.x (xx.xx)
		Median		xx.x	xx.x
		Min, Max		xx, xx	xx, xx
	Adherence (%) CRF				
	< 80%	n/N (%)		xx/xx (xx.x)	xx/xx (xx.x)
	≥ 80% and ≤ 120%	n/N (%)		xx/xx (xx.x)	xx/xx (xx.x)
	> 120%	n/N (%)		xx/xx (xx.x)	xx/xx (xx.x)

[1] Adherence is reported in the CRF and derived directly for each patient using the following formula: Adherence (%)=100\*(actual doses taken/planned dose).

[2] A patient who has taken at least 80% and no more than 120% of the required study medication intake since the last visit will be considered as compliant.

[3] Values for Adherence CRF and Adherence Derived for Combined IP (ZOF/AML) are presented at Visits 3 and 4 under the corresponding AML columns (AML 5 mg at Visit 3, AML 5 mg at Visit 4 for patients on the ZOF/AML 30/5 mg regimen, and AML 10 mg at Visit 4 for patients up-titrated to the ZOF/AML 30/10 mg regimen). Source: Listings 16.2.5.1, 16.2.5.2, 16.2.5.3

Program Name: XXXX.SAS

